Missing Data: Patients who refuse to return for follow-up or who cannot be located and/or do not formally withdraw consent are described as "missing data." Sites will be instructed to continue efforts to contact these patients. See Statistical Plan for more information on how missing data will be handled in the analysis.

Osteolysis: As defined in Exhibit 3: Radiographic Protocol.

Other Interventions: This category includes other surgeries the patient incurs while enrolled in the study that are seemingly unrelated to the implanted device. This would include surgeries such as cholecystectomy, appendectomy, coronary artery bypass surgery, etc.

Revision: A procedure that removes part of the original implant configuration, with or without replacement of the entire component configuration.

Removal: A procedure where the entire original system configuration is removed.

Reoperation: Any surgical procedure that does not include removal or revision, for example, drainage of a hematoma at the surgical site.

Screen Failure: A patient who is either screened but not consented, consented but not randomized or randomized but does not receive the investigational or control device.

Adverse Event (AE): Any event occurring in a study subject that, in the opinion of an M.D. or other qualified and trained medical professional, represents an untoward medical occurrence that differs in either nature, severity, or frequency from a normal post-operative finding. AEs may not have an apparent causal relationship with the device. An AE can therefore be any discrete or ongoing unfavorable and unintended sign (including an abnormal laboratory finding), symptom, or disease temporally associated with the use of a product.

Serious Adverse Event: Any untoward medical occurrence that:

- Results in death
- Is life-threatening
- Requires in-patient hospitalization* or prolongation of existing hospitalization
- Results in persistent or significant disability/incapacity
- Results in congenital anomaly/birth defect

*A planned hospitalization for a pre-existing condition, or a procedure required by the protocol, without a serious deterioration in health is not considered to be a serious adverse event.

Unanticipated Adverse Device Event: any serious adverse event that is or may possibly be related to the device other than those listed in Section C: Risk Analysis or in the institution's approved Informed Consent.

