The three co-primary endpoints for this study are:

- a. ASES score at 22+ Months
- b. No unanticipated device-related adverse event, and no fracture, perforation of the bone or joint dislocation, and no fracture, perforation or dissociation of the device, and no revision or removal of any component, and
- c. Radiographic Success, as defined by:
 - a. Subsidence of the humeral component < 5 mm, and
 - b. Migration of the humeral component < 5mm, and
 - c. No progressive lucency around the humeral component >2mm in two or more contiguous zones
 - d. Migration of the glenoid component <5 mm, and
 - e. No progressive lucency >2mm around the entire glenoid component

SECONDARY ENDPOINTS

The data collected will also be analyzed for the following secondary endpoints:

- 1. American Shoulder and Elbow Surgeon's Score (ASES) at all time points
- 2. Single Assessment Numeric Evaluation (SANE) Score at all time points
- 3. Constant Score at all time points, except 6 weeks (adjusted for age and gender)
- 4. Radiographic assessment of radiolucencies and subsidence
- 5. Overall adverse events including removal/revision and other serious adverse events

The safety of the system will be monitored by recording adverse events including serious adverse events not considered UADEs throughout the follow-up period. Types of events to be collected include but are not limited to:

- Device removal or revisions
- Unanticipated adverse device events
- Systemic adverse events
- Local adverse events
- Reoperations and Other Interventions

Study participants will only be considered discontinued/withdrawn for the following reasons:

- Death
- Withdrawal of consent (written)
- Revision/Removal

Information from any patient who fails to return for multiple, consecutive, scheduled follow-up visits for any reason other than the criteria listed above will be identified as Missing Data.

ANTICIPATED CHANGES

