It is possible that during the course of the study, certain changes may become desirable, although none are anticipated at this time. All changes to the investigation require prior approval from the investigator's Institutional Review Board (IRB) or Ethics Committee (EC) and if necessary, the FDA. Any other deviation from the stated protocol will be considered as such and will be reported accordingly. Since TSA is an elective procedure, it is not expected that treatment will require administration in an emergency setting, therefore all changes to the protocol require review and approval by the investigator's IRB prior to implementation.

RADIOGRAPHIC PROTOCOL

A detailed radiographic protocol is contained in Exhibit 3.

STATISTICAL ANALYSIS PLAN

This is a two-group, multi-center, randomized single blinded clinical trial to compare Total Shoulder Arthroplasty with Biomet's Comprehensive[®] Shoulder System with nano humeral component to another active intervention, a Total Shoulder Arthroplasty with Comprehensive[®] Shoulder System with mini stem component (abbreviations: Investigational vs. Control).

PRIMARY STATISTICAL HYPOTHESES AND DEFINITION OF STUDY SUCCESS

This study is designed to show that the Investigational device is non-inferior to the control device using three co-primary study endpoints. This will be shown using a closed testing method in which each of the primary endpoints specified below are compared using α =0.05. Study success requires that the Investigational group successfully demonstrate non-inferiority when compared to the Control group for all three of the individual primary endpoints, using the statistical methods described below. Because non-inferiority must be successfully shown for all three endpoints for study success, the type I error rate is preserved at 5% for the entire primary endpoint.¹

The individual non-inferiority hypotheses for each of these three tests are as follows:

Radiographic Success

The proportion of successful outcomes (i.e., patients meeting radiographic success criteria) in the Investigational group is non-inferior to the proportion of successful outcomes in the Control group using a 10% margin of non-inferiority. The test is based on the lower bound of a one-sided 95% confidence interval for the difference, Investigational minus Control, in proportions of success at 22+ months. A conclusion of non-inferiority is supported if the lower bound of the confidence interval is at least -0.10.

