Absence of Revision/Removal/UADE

¹ Dmitrienko, Alex, et al. *Analysis of Clinical Trials Using SAS.* SAS Publishing, 2005, pp75-76.

The proportion of successful outcomes (i.e., patients not requiring a revision/removal of any device component or receiving a UADE during the course of the study) in the Investigational group is non-inferior to the proportion of successful outcomes in the Control group using a 10% margin of non-inferiority. The test is based on the lower bound of a one-sided 95% confidence interval for the difference, Investigational minus Control, in proportions of success at 22+ months. A conclusion of non-inferiority is supported if the lower bound of the confidence interval is at least -0.10.

American Shoulder and Elbow Surgeons Score

The mean American Shoulder and Elbow Surgeons (ASES) Score for the Investigational group is non-inferior to the mean ASES score for the Control group using a 9.5-point margin of noninferiority. This margin is based on an approximation that is sometimes used for the MCID based on the observation that for many patient-reported outcome measures, the MCID is about half the SD of change². This method is mentioned as well in an article by Singh et. al, where a half-standard deviation is mentioned as a generally accepted clinically significant benchmark³. Information about plausible values of the standard deviations ASES scores are available in an article by Angst, et. al.⁴ This article gives a standard deviation of postoperative ASES score for 142 subjects of 19.0 points, giving a half-standard-deviation of 9.5 points.

This test will be based on the lower bound of a one-sided 95% confidence interval for the difference, Investigational minus Control, in means at 22+ months. A conclusion of non-inferiority is supported if the lower bound of the confidence interval is at least -9.5 points.

RANDOMIZATION DETAILS

Study: Comprehensive® nano

² Murray et al. "The use of the Oxford hip and knee scores." *JBJS(Br)*. 2007; 89-B 1010-14.

³ Singh, Jasvinder et. al. "Challenges with health-related quality of life assessment in arthroplasty patients: Problems and solutions". *J Bone Joint Surg* 2010; 18:72-82.

⁴ Angst et. al. "Responsiveness in Shoulder Arthroplasty Outcome Instruments." Arthritis & Rheumatism (Arthritis Care & Research) Vol. 59, No. 3, March 15, 2008, pp 391–398

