Information on plausible values of the percentage of patients projected to be radiographic failures was found by looking in the literature to find plausible rates for each component of the radiographic failure definition. Subsidence and migration of the humeral component and progressive radiolucency around the humeral component have been reported at approximately 2% and 0%, respectively. Migration of the glenoid component and progressive lucency of the glenoid component have been reported at approximately 5% and 6%, respectively⁶. Because some overlap is to be expected, the overall Radiographic Success rate is estimated to be 93% for sample size calculation purposes.

Assumptions:

α = 0.05	Probability of Type I error
β = 0.10	Probability of Type II error: power = $1 - \beta$
$p_{C} = p_{I} = 0.93$	Estimated success rate for Control and Investigational groups
δ = 0.10	Non-inferiority Margin

⁶ Sperling,et al. "Radiographic assessment of ingrowth total shoulder arthroplasty." *JBJS.* November/December 2000, Vol 9 No. 6, p 507-513.

Resulting sample sizes (number of shoulders), not adjusted for attrition, are 112 Investigational vs. 112 Control (5% type I error rate, 90% power). The sample size was increased by 15% to allow for possible attrition. This gives a sample size of 264 total subjects (132 Investigational and 132 Control).

Absence of Revision/Removal/UADE

Non-inferiority sample size calculations were implemented in nQuery Advisor 7.0 software using a 1:1 ratio of Investigational to Control subjects. This software uses methodology as described in a text by Farrington and Manning⁷.

The sample size needed to obtain 90% power for testing for non-inferiority of the investigational device to the control device with regard to Absence of Revision/Removal/UADE was calculated as follows:

Definitions:

p_I : Proportion of shoulders in the Investigational treatment group without a

Revision/Removal/UADE

 p_C : Proportion of shoulders the Control treatment group without a Revision/Removal/UADE δ : Non-inferiority margin. Lower 95% confidence bound for difference in proportions of clinically successful subjects at 22+ months (Investigational – Control) must be greater than $-\delta$.

For a specified constant, $0 < \delta < 1$, the hypotheses of non-inferiority are:

$$H_0: p_I - p_C \le -\delta vs. \quad H_A: p_I - p_C > -\delta.$$

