Information on plausible values of the percentage of patients with a revision was found in an article by Jost, et. al. on subjects with Biomet Comprehensive mini-stem shoulder device⁸. A

⁷ Farrington and Manning. "Test statistics and sample size formulae for comparative binomial trials with null hypotheses of non-zero risk difference for non-unity relative risk". *Statistics in Medicine* 9(1990) pp 1447-1454.

total of 49 patients underwent shoulder replacements with the TESS humeral prosthesis with minimum follow-up 2 years. One implant was revised, resulting in a revision rate of 2.0%.

Fracture/perforation of bone, joint dislocation, and dissociation of the device have been reported at approximately 2%⁹, 1%¹⁰ ¹¹, and 0¹²% respectively. Fracture/perforation of the device is not expected to occur and so is estimated at 0%, Using this information, overall success rate is estimated to be 95% (2%+2%+1%) for sample size calculation purposes.

Assumptions:

$\alpha = 0.05$	Probability of Type I error
β = 0.10	Probability of Type II error: power = $1 - \beta$
$p_{C} = p_{I} = 0.95$	Estimated success rate for Control and Investigational groups
δ = 0.10	Non-inferiority Margin

Resulting sample sizes (number of shoulders), not adjusted for attrition, are 82 Investigational vs. 82 Control (5% type I error rate, 90% power). The sample size was increased by 15% to allow for possible attrition. This gives a sample size of 194 total subjects (97 Investigational and 97 Control).

⁸ Jost, Patrick et. al. "Total Shoulder Arthroplasty Utilizing Mini-Stem Humeral Componts: Technique and Short-Term Results." *Hospital For Special Surgery Journal* (2011).

⁹ Bohsali, et. al. "Complications of Total Shoulder Arthroplasty." *JBJS.* 2006 Volume 88-A Number 10, p 2279-2292.

¹⁰ Pfahler, et. al. "Hemiarthroplasty versus total shoulder prosthesis: Results of cemented glenoid components." *J Shoulder Elbow Surg* March/April 2006, p 154-163.

¹¹ Boyd, et. al. "Total Shoulder Arthroplasty vs Hemiarthroplasty." *Journal of Arthroplasty*. December 1990, Vol 5 No. 4, p 329-336.

¹² Blevins, et. al. "Dissociation of modular humeral head components: A biomechanical and implant retrieval study." J Shoulder Elbow Surg March 1997, Volume 6 Issue 2, p A1.

American Shoulder and Elbow Surgeons(ASES) Score

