As with any surgical procedure, there are risks involved with total joint replacement surgery. Potential adverse events include, but are not limited to:

- 1. Complications resulting from anesthetic
- 2. Damage to nerves and blood vessels
- 3. Allergic reactions to the implanted devices
- 4. Phlebitis
- 5. Long-term swelling
- 6. Pulmonary embolus
- 7. Delayed wound healing
- 8. Prolonged illness
- 9. Hematoma
- 10. Wound dehiscence and/or drainage
- 11. Excessive bleeding that may result in the need for blood transfusions and/or further surgery
- 12. Permanent pain, deformity; and inconvenience.
- 13. Permanent brain damage
- 14. Pneumonia
- 15. Venous thrombosis
- 16. Heart attack
- 17. Kidney failure

GENERAL RISKS ASSOCIATED WITH TOTAL SHOULDER REPLACEMENT

- 1. Early or late infection perhaps necessitating device removal
- 2. Component dislocation and subluxation
- 3. Fracture or perforation of the bone (intraoperative or post operative)
- 4. Fracture, perforation, delamination (failure of the porous coating materials to adhere to the implant) of the device (intraoperative or post operative)
- 5. Device loosening or migration
- 6. Fretting or corrosion of implant interfaces
- 7. Wear and/or deformation of articulating surfaces
- 8. Particulate wear debris may initiate a cellular response leading to osteolysis
- 9. Damage to surrounding tissues, cartilage, or tendons
- 10. Inadequate range of motion
- 11. Persistent pain
- 12. Implantation of the device may require greater surgical exposure and prolonged surgical time
- 13. Instability
- 14. Periarticular calcification or ossification, with or without impediment of joint mobility
- 15. Undesirable shortening of limb
- 16. Disassociation of humeral head from humeral stem/component
- 17. Reoperations of the index shoulder to address post operative soft tissue pathologies (eg. Exploration of the brachial plexus, soft tissue release, long head of bicep pathology, rotator cuff tearing including subscapularis rupture/insufficiency, or soft tissue instability)

Rarely some adverse events may be fatal. These possible adverse events are not unique to the Comprehensive[®] Shoulder System with nano humeral component and, as stated above, may occur with any total joint replacement surgery.

Limitation may be imposed depending upon the patient's age, general health, baseline (preoperative) activity level and baseline (pre-operative) condition of the shoulder and other joints.

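### Co-primary endpoint (b) has two definitions: the SAP hypothesis leaves out fractures, perforations, dislocations and dissociations that the protocol counts as failures

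*Combined protocol and SAP*

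**What the plan says.** - **Protocol, Co-Primary Endpoints, item b.** Success requires no unanticipated device-related event and no revision or removal, "and no fracture, perforation of the bone or joint dislocation, and no fracture, perforation or dissociation of the device".
- **SAP, Primary Statistical Hypotheses, Absence of Revision/Removal/UADE.** The successful outcome is spelled out, after an i.e., as "patients not requiring a revision/removal of any device component or receiving a UADE during the course of the study". No other event is mentioned.
- **SAP, Sample Size Calculation, same endpoint.** The control proportion is defined as "Proportion of shoulders the Control treatment group without a Revision/Removal/UADE". The text then adds rates for revision, for bone fracture or perforation and for dislocation: "overall success rate is estimated to be 95% (2%+2%+1%) for sample size calculation purposes". Dissociation and device fracture or perforation enter at 0%.
- **SAP, Definition of Study Success.** Non-inferiority must be shown "for all three of the individual primary endpoints, using the statistical methods described below".
- **Study Definitions.** A UADE is "any serious adverse event that is or may possibly be related to the device other than those listed in Section C: Risk Analysis". Events named in the site's consent form are excluded as well.
- **Section C, General Risks Associated with Total Shoulder Replacement.** The list includes "Fracture or perforation of the bone (intraoperative or post operative)" and "Component dislocation and subluxation", as well as fracture or perforation of the device and separation of the humeral head from its component.

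**The concern.** The protocol and the tested hypothesis classify the same shoulder differently. One with a fracture, dislocation or dissociation that is treated without revision fails item b but counts as a success in the SAP hypothesis. No section says which definition governs the analysis.

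Because all three co-primary tests must pass, this choice can decide the study. If the SAP wording is followed, the omitted events are compared only as safety outcomes, which the Significance Levels section treats as exploratory. If the choice is made after results are seen, it is open to the charge that it followed the data.

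The gap is limited. Loosening or migration, the risk that Section C singles out for the nano component, would be caught by revision or by Radiographic Success. What is exposed is the unrevised fracture, dislocation or dissociation.

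**Working it through.** **1. Can the UADE term recover the omitted events?** No. The UADE definition excludes anything listed in Section C, and Section C lists bone and device fracture or perforation, dislocation and head dissociation.

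**2. Which definition did the planning use?** Inputs from the sample-size section are success 0.95 in both arms, margin 0.10, one-sided alpha 0.05, power 90% and attrition 15%. With unpooled variance,

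n = (1.645 + 1.282)² × 2 × p(1 − p) / 0.10²

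- p = 0.95: 8.564 × 0.095 / 0.01 = 81.4, so 82 per arm; 82 / 0.85 = 96.5, so 97. Both match the plan.
- p = 0.98 (2% revision only, UADE assumed 0%): 8.564 × 0.0392 / 0.01 = 33.6, so 34 per arm; 34 / 0.85 = 40.

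The plan's figure follows from the composite rate. Three of the five percentage points of expected failure (2% bone fracture or perforation, 1% dislocation) are events that the SAP hypothesis does not count.

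**3. Can one data set give two verdicts?** The SAP's Wald rule, written as investigational minus control, is

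lower bound = (p_I − p_C) − 1.645 × √[p_I(1 − p_I)/n + p_C(1 − p_C)/n], pass if at least −0.10.

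Take n = 112 per arm, the evaluable number before attrition is added.

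| Definition | Failures, nano v control | Lower bound | Result |
|---|---|---|---|
| Composite | 10 v 5 | −0.099 | pass |
| Composite | 11 v 5 | −0.110 | fail |
| SAP wording, none of the 6 excess failures revised | 2 v 2 | −0.029 | pass |
| SAP wording, half revised | 5 v 2 | −0.065 | pass |
| SAP wording, all revised | 8 v 2 | −0.099 | pass |

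For 11 v 5: −6/112 − 1.645 × √(0.000791 + 0.000381) = −0.0536 − 0.0563 = −0.110. The 11 v 5 case was chosen because it lies at the boundary.

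**4. How often would the verdicts differ?** The assumptions are UADE 0%; 2% of control shoulders revised and a further 3% with an unrevised event; no overlap; and s, the share of excess nano failures that is revised. Under the SAP wording, nano success is then 0.98 − s × (0.95 − composite success). Pass rates come from exact binomial enumeration. Same-trial disagreement comes from 400,000 simulated trials per scenario, n = 112 per arm. Control composite success is 95% throughout.

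| True nano composite success | Composite test passes | SAP wording passes, s = 0 / 0.5 / 1 | SAP wording passes and composite fails, s = 0 / 0.5 / 1 |
|---|---|---|---|
| 95% (equal arms) | 95.9% | 99.9% | 4% |
| 92% | 70% | 99.9 / 97 / 86% | 30 / 28 / 19% |
| 90% | 44% | 99.9 / 91 / 58% | 56 / 47 / 19% |
| 88% | 23% | 99.9 / 80 / 30% | 77 / 58 / 12% |
| 86% | 10% | 99.9 / 66 / 12% | 90 / 56 / 6% |
| 85% | 6% | 99.9 / 58 / 7% | 94 / 52 / 4% |

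The reverse disagreement (composite passes, SAP wording fails) never exceeds 4.7%.

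**The case against.** The best defence is that Absence of Revision/Removal/UADE is a short label for the item b composite. The sample-size section uses the label in just that way, setting it over a rate that includes fractures and dislocations. On this view the text after i.e. is an incomplete gloss, and the composite was never dropped. It is true that the label alone proves little. But the hypothesis states its own content, whereas the Radiographic Success hypothesis simply refers to its criteria. A programmer working from the SAP would follow the stated content.

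The second objection concerns the probabilities, and much of it stands. True composite rates of 86% to 92% against 95% lie inside the 10-point margin, so disagreement there is not a false claim of non-inferiority; the composite test is failing for lack of power. Only 85% v 95% sits on the margin, and the documents give no reason to expect it. Under the plan's own assumption of equal arms, disagreement is 4%; at 94% v 95% it is 9% to 10%. The revised share and the absence of overlap are assumptions, and nothing in the documents suggests an excess of unrevised fractures or dislocations with nano.

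Third, the composite wording is itself terse. It does not say how intraoperative events count, and the independent adjudicator's stated task is relationship to device or procedure. That makes the fix somewhat longer but does not remove the conflict.

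**Conclusion.** The concern holds. The protocol's endpoint and the SAP's tested hypothesis differ in current text, the UADE definition does not bridge them, and the two rules can return opposite verdicts on the same data. This is an error in a success-determining rule and must be corrected.

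The size runs from slight to large. Disagreement is about 4% with equal arms. It rises to 19% to 56% at 90% v 95% composite success, according to how many excess failures are revised. At 85% v 95%, where the composite test passes 6% of the time, the SAP wording passes 99.9%, 58% or 7% of the time with none, half or all of the excess revised. So error control for the composite is lost unless nearly all of the excess is revised.

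These figures concern endpoint (b) alone at 112 per arm, under the assumptions listed with the calculation. The effect on the joint three-endpoint verdict was not computed.

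**What to change.** Before outcomes are compared by arm:

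1. In the SAP hypothesis for this endpoint, replace the i.e. text with the item b composite. Do the same in the definitions of p_I and p_C in the sample-size section.
2. Align the short labels in the Study Summary and the sensitivity-analysis table, or state that they denote the composite.
3. State how intraoperative bone fracture or perforation is counted, since Section C lists both intraoperative and postoperative events.
4. As minor clarifications under Analysis Population and Missing Data, say that device failure means any component of (b) and that such shoulders enter the Analysis Population for (b). Also say how a revision between 24 and 26 months without a 22+ month film is classed for Radiographic Success; the cut-off is the sponsor's choice.

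Cost: a wording amendment, with IRB approval and FDA approval if necessary. The total stays at 264 because Radiographic Success sets it, and 82 (97 after attrition) per arm already matches the composite. Expected success for (b) is 95% rather than 98%, which is the rate already planned. The protocol requires all adverse events to be reported and operative complications to be recorded. The case report forms (Exhibit 4) were not available, so their fields should be checked for each component.
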